Phase	N/A, This is not a clinical trial, it is one of imaging modalities
Methodology/Study Design	Prospective, non-randomized, double blind study
Study Duration	2 years
Study Center(s)	Single-center
Objectives	In this study, we aim to explore which imaging modality or combination of imaging methods, in conjunction with clinical and histological examination, will most accurately predict the presence or absence of invasion of the mandible or maxilla by intraoral squamous cell carcinoma (SCC)
Number of Subjects	20
Diagnosis and Main Inclusion Criteria	Inclusion: SCC of the oral cavity Exclusion: prior mandibular surgery, primary intraosseous carcinoma, prior history of radiation to the mandible, obvious finding of clinical invasion of the mandible, age under 18 years old
Study Therapy, Dose, Route, Regimen	N/A
Duration of administration and follow-up	N/A
Reference therapy	N/A
Statistical Methodology	Sensitivity and specificity of mandibular or maxillary invasion will be determined, in addition to true and false positive as well as true and false negative. Finally the positive and negative predictive values for each of the imaging modalities will be calculated based upon the previously mentioned statistical analysis.
Schema	See attached schema in the appendix section at the end

1.0 INTRODUCTION

This document is a protocol for a human research study. This study is to be conducted according to US and international standards of Good Clinical Practice (FDA Title 21 part 312 and International Conference on Harmonization guidelines), applicable government regulations and Institutional research policies and procedures.

1.1 Specific Aims and Hypothesis

There are newer imaging modalities that have not been studied sufficiently to determine whether intraoral SCC has or has not infiltrated a segment of the mandible or maxilla, necessitating partial or complete resection of the jaw. One such modality is cone beam CT (CBCT), which delivers approximately 1/6 the amount of radiation and is about 1/10 the cost of a multi-slice, helical CT¹. A previously published imaging protocol by Van Cann et al² used MRI, CT and bone SPECT to image the mandible. In contrast to the prior algorithm, this study aims to test newer modalities such as the CBCT, PET/CT and helical CT against more traditional imaging techniques, to attempt to detect neoplastic infiltration of the mandible and maxilla. We hypothesize that CBCT or a combination of the aforementioned modalities can be used in order to more accurately predict invasion of the maxilla or mandible by intraoral SCC.

The accurate prediction of the presence or absence of malignant invasion of the jaws greatly influences the surgical treatment plan. This is important for several reasons. First, it may change the staging of the disease, necessitating a more or less involved resection and reconstruction. Second, this knowledge will greatly benefit the surgeon, since the reconstruction of an extensive surgical defect will be more complex and require greater planning. In addition, occult infiltration of the jaws may be a source of locoregional regrowth and recurrence that may be detectable by such imaging, leading to a wider, more appropriate and oncologically sound resection. Third, if absence of mandibular or maxillary invasion can be proven statistically, it will permit “sparing” of complete or partial resection. Thus, the mandible and maxilla, which are critical to facial form and function, will be preserved in some form and improve the overall quality of life of the cancer patient.

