3.2 Primary Study Endpoints

The primary endpoint is to determine if any one or combination of imaging modalities can accurately predict the presence or absence of bone invasion by oral squamous cell carcinoma

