7.2 Statistical Methods

Sensitivity and specificity of the clinical exam, CBCT, helical CT, PET/CT, MRI and any other imaging modality used in detection of bone invasion will be calculated, as compared to the histological examination of the specimens.

Sensitivity: $[TP / (TP + FN)] \times 100$

Specificity: $[TN / (FP + TN)] \times 100$

Also, the confidence interval will be determined for the sensitivity and specificity.

True positive (TP): pts with histologic and radiographic evidence of invasion

True negative (TN): pts without histologic or radiographic evidence of

invasion

False Positive (FP): pts with positive radiologic evidence of invasion without histologic evidence

False Negative (FN): Those without radiographic evidence of invasion, but with histologic invasion present

In addition, the positive and negative predictive value will be calculated for each modality using the true positive and negatives as well as false positive and negative values.

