8.3 Unblinding Procedures

If it is found that any one or combination of imaging studies is able to accurately predict the presence or absence of bone invasion, this information will be unblinded to the oncologic surgeon, thereby allowing them to use the information in planning their surgical resection

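### The plan asks which modality or combination is most accurate but sets no combination rule, comparator or joint criterion, so an uninformative added scan can often look like an improvement on one measure

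*Combined protocol and SAP*

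**What the plan says.** The hypothesis in 1.1 is comparative and covers combinations: "We hypothesize that CBCT or a combination of the aforementioned modalities can be used in order to more accurately predict invasion of the maxilla or" […]. Section 2.1 makes it the primary objective to find the modality or combination that predicts most accurately. The primary endpoint in 3.2 is to "determine if any one or combination of imaging modalities can accurately predict the presence or absence of bone invasion".

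The planned analysis is in 7.2. It covers "Sensitivity and specificity of the clinical exam, CBCT, helical CT, PET/CT, MRI and any other imaging modality used in detection of bone invasion", each against histology. It adds that "the confidence interval will be determined for the sensitivity and specificity", and that "the positive and negative predictive value will be calculated for each modality". The Study Summary lists the same quantities together with the true and false positive and negative counts. Positivity is defined for one reading only; a true positive, for example, is "pts with histologic and radiographic evidence of invasion". Neither place says how several scans are merged into one call, what a modality or combination is compared with, or which measure settles the question of accuracy.

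Section 8.3 attaches a consequence to the finding. It begins "If it is found that any one or combination of imaging studies is able to accurately predict the presence or absence of bone invasion", and then releases the information to the surgeon for planning the resection. It gives no criterion either.

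**The concern.** The main question is a ranking, and the listed analyses cannot produce one. Four one-sided measures per modality do not show whether one modality is more accurate than another when one gains sensitivity and loses specificity. For combinations the gap is worse, because the two obvious ways of merging binary reads each protect one measure by arithmetic:

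- *Any positive*: every patient called positive by a component stays positive, so observed sensitivity cannot fall below that of any component.
- *All positive*: every patient called negative by a component stays negative, so observed specificity cannot fall below that of any component.

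Both hold whether or not the added scan carries information. With rule and measure left open, a report could describe a combination as better at detecting, or at excluding, invasion when overall discrimination has fallen. Under 8.3 a finding of accuracy is what unblinds imaging to the surgeon.

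**Working it through.** There is no figure of the plan's own to reproduce. N=20 (Study Summary) rests on case volume (7.1), and the appendix shows N=10. The documents give no prevalence, accuracy, significance level or margin, so the values below are assumptions.

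**Inputs (assumed).** N=20 with 6 invaded and 14 not. Scan A has sensitivity Se and specificity Sp of 0.80. Scan B is noise, read positive with probability q=0.30 whatever the histology. Reads are independent given histology.

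**True performance (J = Se + Sp − 1, the Youden index).**

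- Scan A alone: J = 0.80 + 0.80 − 1 = 0.60.
- Any positive: Se = 0.80 + 0.20×0.30 = 0.86; Sp = 0.80×0.70 = 0.56; J = 0.42.
- All positive: Se = 0.80×0.30 = 0.24; Sp = 0.80 + 0.20×0.70 = 0.94; J = 0.18.

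Each rule gains on one measure and loses discrimination.

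**Chance of a strict observed gain over scan A.**

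- Sensitivity under *any positive*: 1 − (1 − 0.20×0.30)^6 = 1 − 0.94^6 = 1 − 0.690 = 0.31.
- Specificity under *all positive*: 1 − (1 − 0.20×0.70)^14 = 1 − 0.86^14 = 1 − 0.121 = 0.88.
- At least one of these: 1 − 0.690×0.121 = 0.916. Simulation gives 0.917.

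**Sensitivity to the assumptions.** The grid has 36 scenarios per N: prevalence 20%, 30% or 50%; base accuracy 0.70, 0.80, 0.90 or 0.95; q of 0.1, 0.3 or 0.5. The chance of at least one gain, with a free choice of rule, is:

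| | Median | Range |
|---|---|---|
| N=20 | 83% | 40% to 99% |
| N=10 | 60% | 22% to 92% |

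At N=20, by base accuracy, the range is 96–99% (0.70), 88–96% (0.80), 64–79% (0.90) and 40–53% (0.95). With one rule and one measure fixed at N=20, the median is 18% for *any positive* on sensitivity and 75% for *all positive* on specificity.

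**With a joint criterion (simulated).** In the base case, the better of the two rules has a higher observed Youden index than scan A in 13.9% of studies, and higher than the better of the two scans in 13.0%. Over the N=20 grid the comparison with scan A gives a median of 6% and a maximum of 29%, at base accuracy 0.70.

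**The case against.** The strongest reply is that the plan never says a gain in one measure confirms the hypothesis. A reader might infer that accuracy is to be judged on sensitivity and specificity taken separately, but the documents state no judging criterion at all. The defect is an omission, not a faulty rule. Likewise, presence or absence of invasion is ordinary wording for a binary status, and 1.1 wants both occult invasion found and uninvolved bone spared. It should not be read as permission to succeed on one side.

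Other points on that side also stand:

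- The loss would be visible. In the base case, a gain on one measure with no loss on the other occurs in only 1.3% of studies, so a careful reader would see the trade-off. With a noise scan, true PPV under *all positive* and true NPV under *any positive* do not improve.
- The high rates need a free choice of rule and measure. They also need the noise to be independent of scan A. If the added scan instead agrees with A in an assumed 90% of patients and otherwise carries nothing about histology, the chance per patient of a favourable change is 0.20×0.10 = 0.02, and the rate is 1 − 0.98^20 = 33%.
- A paired test would seldom support the false gain. An exact two-sided 5% McNemar test needs at least 6 one-way changes. In the base case that has a chance of 0.06^6, about 5 in 10^8, for sensitivity, and about 0.8% for specificity.

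These points limit the claim but do not remove it. The plan leaves the choice of rule open and specifies no paired comparison. Nothing in it requires the gain and the loss to be weighed together.

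**Conclusion.** The concern holds in a limited form. Sections 1.1, 2.1 and 3.2 ask which modality or combination is more or most accurate; 7.2 and the Study Summary cannot answer that as written. With a freely chosen any/all rule, an uninformative scan can often appear to improve one planned measure: about 92% in the base case, about 40% to 99% over the N=20 grid, and 31% in the base case if only *any positive* judged on sensitivity is allowed. Requiring a higher Youden index brings the base case to 13–14%, and up to about 29% at base accuracy 70%. All of these rest on assumed prevalence, accuracy, noise rate and independence.

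Three stronger readings are tempting and are not supported:

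- That every combination wins by construction. Only the absence of a loss is guaranteed, and only for any/all rules. A majority rule joining the 80% scan with two noise scans at q=0.5 falls to 0.65 on both measures.
- That a useless scan will usually appear to confirm the hypothesis. This depends on the assumptions, and the documents set no criterion for confirmation.
- That a paired comparison would not help. The McNemar figures show that it would.

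**What to change.** In 2.1, 3.2 and 7.2:

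- Name in advance the combinations to be assessed and the positivity rule for each (any or all). Treat all others as exploratory.
- Compare each combination with its best single component in the same patients. Section 5.4 gives every patient helical CT, PET/CT and CBCT, so paired data for these three are already planned.
- Show the paired differences in sensitivity and specificity together, with a joint summary such as the Youden index and a paired 95% interval.
- State that a combination will not be called more accurate on a gain in sensitivity, specificity, PPV or NPV alone.

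In 3.2 and 8.3, make clear that accurate prediction refers to both presence and absence of invasion.

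The cost is protocol wording and a few lines of analysis, with no extra patients, scans or readers. There are two downsides. The Youden index weights missed invasion and false alarms equally, which is a value choice, so both components must stay in the report. Fewer combinations will look better. For example, adding an informative scan (80% sensitivity, 95% specificity) to the 80%/80% scan beats the best component in about 32% of simulated studies. That is reasonable: the second scan alone has a true Youden index of 0.75, against 0.72 for *any positive* and 0.63 for *all positive*.

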1.2 Background and Rationale

In 2008, Van Cann et al² published a protocol of assessment of mandibular invasion by intraoral SCC. This algorithm involved using a combination of MRI, bone SPECT and helical CT. In 2010, Hendrikx et al³ examined CBCT to determine its ability to predict invasion of the mandible by carcinoma. They found that CBCT has the potential to obviate unnecessary mandibular resection and that it warranted further evaluation as such a tool. Review of CBCT literature shows two other studies that examined CBCT for the

detection of mandibular invasion by SCC^{1,4}. These studies have been retrospective in nature and none of them have examined the maxilla for possible invasion by SCC. Thus, this study will compare CBCT, PET/CT, and helical CT of the maxilla and mandible in a prospective manner with a larger study cohort than previous studies.

The accurate prediction of the presence or absence of mandibular or maxillary infiltration by SCC will allow use of 3-D surgical planning models for the immediate reconstruction of the defect and preclude prolonged loss of function that patients may experience post-resection.

1.3 Study Therapy

This is a study comparing radiologic modalities already in use as the standard of care in order to determine bone invasion by oral squamous cell carcinoma.

1.4 Preclinical Data

Summarize the available non-clinical data (published or available unpublished data) that could have clinical significance.

Refer to section 1.2 “Background and Rationale”

1.5 Clinical Data to Date

Summarize the available clinical study data (published or available unpublished data) with relevance to the protocol under construction.

Refer to section 1.2 “Background and Rationale”

2.0 STUDY OBJECTIVES

2.1 Primary Objective:

To determine which imaging modality or combination of imaging methods, in conjunction with clinical and histological examination, will most accurately predict the presence or absence of invasion of the mandible or maxilla by intraoral squamous cell carcinoma (SCC).

2.2 Secondary Objective:

To compare the histopathologic findings to the radiologic findings

3.0 STUDY DESIGN

3.1 General Design

Prospective, non-randomized, double blinded study

3.2 Primary Study Endpoints

The primary endpoint is to determine if any one or combination of imaging modalities can accurately predict the presence or absence of bone invasion by oral squamous cell carcinoma

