5.4 Method for Assigning Subjects to Treatment Groups

This study will not be randomized. All patients will received a helical CT, PET/CT and CBCT

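### The accuracy figure for whichever modality is named best is biased upward, because the same few patients select it and estimate it with no allowance for the selection

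*Combined protocol and SAP*

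**What the plan says.** Section 2.1 makes selection the primary objective: "To determine which imaging modality or combination of imaging methods, in conjunction with clinical and histological examination, will most accurately predict" invasion of either jaw. Section 3.2 words the primary endpoint as whether the study can "determine if any one or combination of imaging modalities can accurately predict the presence or absence of bone invasion". It gives no threshold for accurate and names no primary test. The hypothesis in section 1.1 is narrower: "We hypothesize that CBCT or a combination of the aforementioned modalities can be used in order to more accurately predict invasion".

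Section 7.2 gives the candidates. One is examination by the clinician, and for the imaging tests the text reads: "CBCT, helical CT, PET/CT, MRI and any other imaging modality used in detection of bone invasion will be calculated". The quantities are sensitivity and specificity against histology, with a confidence interval for each. Predictive values follow for each modality. The section lists no combinations, no rule for combining tests and no measure for ranking them. Section 5.4 fixes only three of the tests for everyone: "All patients will received a helical CT, PET/CT and CBCT".

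Section 7.3 analyses all enrolled, consented subjects, without a hold-out set, cross-validation or correction for optimism. The Study Summary gives "Number of Subjects 20", while the appendix shows a cohort of 10. Section 7.1 bases the number on yearly caseload. Section 8.3 attaches a consequence, which begins "If it is found that any one or combination of imaging studies is able to accurately predict the presence or absence of bone invasion".

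**The concern.** When several tests are measured in the same small sample and the best is picked, part of its lead is chance. Its observed figure is the maximum of several noisy estimates, which on average exceeds the true value of the test picked. An ordinary confidence interval treats the test as if it had been chosen beforehand, so it does not allow for the picking. This happens with three single scans alone, so defining combination rules would not remove it.

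The stake is the answer to the primary objective. A reader would take the winner's figure as its expected performance in new patients, and the ranking as established, when in a sample this small both may be partly chance. Section 8.3 relies on the same uncorrected finding.

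**Working it through.** **Inputs from the documents.** N = 20 (Study Summary), or 10 (appendix). Three scans for every patient (5.4). Five named tests (7.2).

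**Assumptions, because the documents give none.** True accuracy 0.75 to 0.90; 6 invaded patients of 20 (30%); errors either independent or correlated through a shared normal variable. Overall accuracy (share of patients classified correctly) is used for illustration, since the plan defines no single ranking measure. The plan has no bias figure of its own to reproduce.

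**Step 1. Equal, independent tests, exact.** Let F be the Binomial(n, p) distribution function. The best of k tests has distribution function F(x)^k, so its expected proportion correct is

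E = 1 − (1/n) × Σ F(x)^k, summed over x = 0 to n − 1.

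For n = 20, p = 0.80, k = 3, the terms for x = 13 to 19 are 0.0007, 0.0075, 0.0508, 0.2039, 0.5004, 0.8065 and 0.9658. Earlier terms are negligible. They sum to 2.5356, so E = 1 − 2.5356/20 = 0.873, a bias of +7.3 points.

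Bias in points for other values:

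| N | k | 0.75 | 0.80 | 0.85 | 0.90 |
|---|---|---|---|---|---|
| 20 | 3 | 8.0 | 7.3 | 6.5 | 5.3 |
| 20 | 5 | 10.8 | 9.8 | 8.6 | 7.0 |
| 10 | 3 | 11.1 | 10.1 | 8.8 | 7.0 |
| 10 | 5 | 14.8 | 13.4 | 11.5 | 8.8 |

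Correlated errors reduce this. At N = 20, k = 3 and correlation 0.5, the bias is 6.1 points at 0.80 and 4.6 at 0.90.

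**Step 2. Unequal tests, simulated.** N = 20, three scans. Bias is the winner's observed accuracy minus the true accuracy of the scan that won.

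| True accuracies | Correlation 0 | Correlation 0.5 |
|---|---|---|
| 0.90, 0.80, 0.80 | 4.8 | 3.6 |
| 0.90, 0.80, 0.70 | 3.7 | 2.6 |
| 0.90, 0.70, 0.70 | 2.3 | 1.3 |

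In the first row the better scan ranks strictly first in only 61% of studies (independent) to 66% (correlation 0.5).

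**Step 3. Sensitivity.** With 6 invaded patients and true sensitivity 0.80 for each of three scans, F(3) = 0.099, F(4) = 0.345 and F(5) = 0.738. Their cubes are 0.001, 0.041 and 0.402, which sum to 0.444. E = 1 − 0.444/6 = 0.926, a bias of +12.6 points. One scan named beforehand shows 6 of 6 with probability 0.8^6 = 0.262. At least one of three does so with probability 1 − (1 − 0.262)^3 = 0.598.

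**Step 4. What a correction recovers.** In each bootstrap resample, pick the best test again and subtract its accuracy in the actual sample from its accuracy in the resample. The mean difference is the optimism, which is subtracted from the apparent figure. With three equal scans at 80%, simulated studies gave a mean apparent 87.7% falling to 83.2%: 87.7 − 83.2 = 4.5 points removed, and 83.2 − 80 = 3.2 left. A repeat with 3,000 studies and 200 resamples each gave 87.3% (the exact value in Step 1) falling to 82.6%, while the standard deviation across studies rose from 6.0 to 7.7 points.

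**The case against.** The strongest reply is that section 7.2 reports every modality and singles out no winner. Full reporting involves no selection and no bias. The Study Summary also describes the aim as exploring. Both statements are true of those passages, but section 2.1 asks which candidate is most accurate, so answering the primary objective requires the picking that 7.2 leaves uncorrected. An exploratory label would not remove the bias from the figure of the test picked.

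Three further objections stand and limit the point:

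- A reader might infer a fixed inflation of 5 to 11 points. The documents do not support that. The range assumes three to five independent tests of equal accuracy, which is close to the worst case for a given number of tests. MRI is not among the scans that section 5.4 gives everyone. The clinical exam is unlikely to match the scans, because section 4.2 excludes obvious clinical invasion of the mandible.
- A reader might infer that the endpoint is met as soon as any candidate looks good. Section 3.2 states no criterion for being met, so no false-success rate follows from it. The 6-of-6 probabilities above are illustrations. Nor would helical CT or PET/CT alone satisfy the hypothesis, which names CBCT or a combination.
- A reader might infer that CBCT has to become the sole primary test. That would replace the comparative question in section 2.1. It is an option with a trade-off.

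**Conclusion.** The concern holds as an inexpensive improvement. Following the plan as written, the figure for any modality or combination named most accurate is biased upward, and its ordinary interval ignores the selection. The direction is not in doubt, but the size depends on assumptions. With 20 patients and three scans, the bias in overall accuracy is about 5 to 8 points if the scans are equally accurate (0.75 to 0.90, independent errors) and about 1 to 5 if one is truly better. It reaches about 11 points with five equal tests and is larger at the appendix cohort of 10. Sensitivity is more exposed, at about 13 points for the best of three in an assumed 6 invaded patients. The ranking is also fragile: a scan truly 10 points better than two others comes strictly first in about 61% to 66% of studies.

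**What to change.** In section 7.2, before histology is linked to imaging:

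1. Fix the list of candidate modalities and combinations, with the rule for combining them, and the measure used to rank them.
2. Report every modality, and describe the ranking as exploratory.
3. For any modality or combination called most accurate, report a bootstrap or leave-one-out optimism-corrected estimate that repeats the selection in each resample, with the share of resamples in which it ranks first.

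The sponsor may also state CBCT, which the hypothesis names first, as the pre-named index test. Its estimate and interval would then need no correction for selection.

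Reconcile the cohort of 20 with the 10 in the appendix. Section 8.3 relies on the same uncorrected finding and must be reconciled with 3.2 and 7.2. This review proposes no rule for it.

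The cost is protocol wording and a short resampling analysis, with no new patients or scans. The downside is a less favourable and more variable figure for the winner. The bootstrap removes only part of the bias, so confirmation in new patients would still be needed.
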